To assess the generalizability of the data from the patients enrolled, the physician will be asked to document on a separate Case Reporting Form the number of patients who are eligible but refuse to participate in the study. Only age ranges (<30 years, 30-45 years, 45-65 and > 65 years) and reason(s) for not participating will be collected.

The primary endpoint of this PMOS will be the percentages of APD patients on LCIG monotherapy right after LCIG initiation and at 3, 6, 9, and 12, respectively.

The secondary endpoints are:

- Descriptive data from patient's PD medication:
 - For add-on PD medication: percentage of patient on each PD medication (by drugs and class), total daily dose and levodopa equivalent Daily dose (LEDD), posology (number of times per day);
 - For LCIG infusion settings and substantial dose adjustments: total dose per day and specific for each type of dose (morning dose and continuous dose) and number of hours of infusion.

- Tapering process: number of days required for the tapering process, total dose per day and posology for add-on PD medication prior to LCIG initiation, at LCIG initiation (titration) or during ongoing LCIG treatment
- Main reasons for introduction or tapering of add-on PD medication or LCIG substantial dose adjustments
- Latency and duration of treatments data:
 - Number of days or months from LCIG initiation until LCIG is given as a monotherapy and the duration of LCIG monotherapy.
 - Number of days or months from LCIG initiation until the introduction or tapering of each PD medication, or until any LCIG substantial dose adjustments.
- LCIG monotherapy vs LCIG plus add-on PD medication data:
 - Healthcare Resource Utilization, as measured by Healthcare Resource Utilization Questionnaire (HCRU)
 - Patient's, caregiver's, and physician's overall preference on LCIG monotherapy vs. LCIG plus add-on PD medication, percentage of patient's and physician's preference for each of the options
 - Predictors for LCIG as monotherapy vs. LCIG plus add-on PD medication based on the patient's profile, including socio-demographics, clinical status (motor and non-motor symptoms), Levodopa-equivalent dose (LED), PD medication and Quality of Life
 - Predictors for LCIG as monotherapy vs. LCIG plus add-on PD medications based on the physician's profile including experience as measured by number of years on APD patient management, number of years using LCIG therapy, and number of patients on LCIG therapy

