#### 6.5 Secondary variables

#### Descriptive data from patient's PD medication

Add-on PD medication:

At the time points LCIG initiation and at 3, 6, 9, and 12 months after LCIG initiation, at visit and at appropriate time points between 12 months after LCIG initiation and the visit:

 Add-on PD medication (multiple answers; category and medication/therapy; patient based)

Category and medication/therapy are as follows:

Category	Medication/therapy
Levodopa	Levodopa/carbidopa Levodopa/benserazide Levodopa/carbidopa/entacapone Other
COMT inhibitor	Entacapone Tolcapone Opicapone Other
Dopamine Agonist (excluding Apomorphine)	Pramipexole Ropinirole Cabergoline Rotigotine Other
MAO Inhibitor	Selegiline Safinamide Rasagiline Other
NMDA Antagonist	Budipine Amantadine Other
Apomorphine	Apomorphine intermittent injection SC Apomorphine subcutaneous continuous infusion 30mg/ml solution Other
Anticholinergics	Anticholinergics Other

Surgical therapy	Pallidotomy Thalamotomy Deep brain stimulation (DBS) Stem Cell Transplant Other
Other	-

- Total daily dose separately for each category and for each medication/therapy (except all 'Other', Anticholinergics, and Surgical therapy; Apomorphine only if possible)
- Levodopa equivalent daily dose (LEDD) separately for each category and for each medication/therapy if applicable (see Section 7.6)
- Total daily LEDD (in mg; see Section 7.6)
- Posology (i.e. average number of intakes per day) separately for each category and for each medication/therapy (except all 'Other' and Surgical therapy)
- Add-on PD medication in categories and medication/therapy (multiple answers)

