#### 7.6 Secondary variables

The secondary variables will be evaluated for FAS.

Secondary variables will be analyzed overall and separately for the following three groups:

- Patients on monotherapy 1 at 12 months after LCIG infusion (see Section 6.4)
- Patients on monotherapy 2 at 12 months after LCIG infusion (see Section 6.4)
- Patients not on monotherapy 2 at 12 months after LCIG infusion (see Section 6.4)

Regarding 'Add-on PD medication' patient based means that a therapy type will only be counted once per patient. The variables total daily dose, LEDD and posology will additionally be analyzed per category by summing up the values of the corresponding medication/therapy.

Regarding total dose per day the difference will be calculated between the time points LCIG initiation start, 12 months after LCIG initiation start and visit as follows:

- Total dose per day at 12 months after LCIG initiation start minus total dose per day at LCIG initiation start
- Total dose per day at visit minus total dose per day at LCIG initiation start
- Total dose per day at visit minus at 12 months after LCIG initiation start

If applicable, levodopa equivalent daily dose (LEDD) will be calculated separately for each medication/therapy as total daily dose in mg multiplied with the respective factor (from Table 7-1; [1], [2], [3]). Exceptions are entacapone, tolcapone and opicapone: irrespective of the entacapone dose (or tolcapone or opicapone dose, respectively) the corresponding levodopa dose is multiplied by the given factor. This will then be considered as LEDD for entacapone (or tolcapone or opicapone, respectively).

The total daily LEDD will be the sum over all daily LEDDs which were calculated separately for each medication at the respective time point.

Table 7-1: Factor for levodopa equivalent daily dose

Medication	Factor
Levodopa/carbidopa	1.11
Levodopa/benserazide	1
Levodopa/carbidopa/entacapone	1.33
Amantadine	1
Apomorphine	10
Cabergoline	80
Entacapone	concomitant levodopa multiplied by 0.33
Tolcapone	concomitant levodopa multiplied by 0.5
Pramipexole	100
Rasagiline	100
Ropinirole	20
Rotigotine	30
Selegiline oral	10
Opicapone	concomitant levodopa multiplied by 0.65
Safinamide	
Budipine	5

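### The class table in SAP 6.5 places levodopa/carbidopa/entacapone under Levodopa only, so the class-level rows for COMT-inhibitor use and LEDD leave out entacapone taken in that tablet

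*SAP*

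**What the plan says.** The protocol's secondary endpoints (section 9.1) include "percentage of patient on each PD medication (by drugs and class"), together with daily dose, LEDD and posology. Reporting by class is therefore required by the protocol, although the protocol does not define the classes.

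SAP 6.5 defines them in a table. The Levodopa category holds "Levodopa/carbidopa Levodopa/benserazide Levodopa/carbidopa/entacapone Other"; the COMT inhibitor category holds "Entacapone Tolcapone Opicapone Other". The fixed combination appears once, under Levodopa. Add-on use is tabulated by category and by medication at LCIG initiation, at 3, 6, 9 and 12 months, at the visit, and at suitable points in between. The variable allows several answers per patient.

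SAP 7.6 adds the counting rule: "Regarding 'Add-on PD medication' patient based means that a therapy type will only be counted once per patient". It does not place the combination in a second class. The same section obtains category dose, LEDD and posology by adding up the medications listed in each category, and obtains total LEDD by adding up all medications. In Table 7-1 the relevant entries are "Levodopa/carbidopa 1.11", "Levodopa/benserazide 1" and "Levodopa/carbidopa/entacapone 1.33"; the entry for entacapone is "concomitant levodopa multiplied by 0.33", and the text treats that product as the LEDD of entacapone.

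**The concern.** Two patients who both take levodopa and entacapone are classified differently according to whether the entacapone comes in a separate tablet. The one on separate tablets counts as a COMT-inhibitor user; the one on the combination does not. A change from one presentation to the other moves the COMT class percentage although the patient is on entacapone throughout.

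The LEDD rule is also inconsistent between presentations. The SAP credits separate entacapone to the COMT class, but when the same contribution is part of the combination's factor, the category sum puts it under Levodopa.

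Medication management before, at and after LCIG initiation is the first secondary objective, and it is repeated for each country with at least 20 patients. A reader of the class table would take the COMT row as the percentage on any COMT inhibitor. It is not, and the error can only be downward.

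**Working it through.** **Inputs.** Class membership comes from the table in SAP 6.5. The factors come from SAP 7.6, Table 7-1: combination 1.33, levodopa/benserazide 1, levodopa/carbidopa 1.11, and entacapone 0.33 × concomitant levodopa. The planned size is about 400 patients (SAP 4.2). The documents do not give the share of patients on the combination, so it is an assumption below.

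**Step 1: reproduce the stated factor.** Unit levodopa factor plus entacapone part: 1.00 + 0.33 = 1.33, which is the factor in Table 7-1. With the levodopa/carbidopa factor the sum is 1.11 + 0.33 = 1.44, which does not match. The 1.33 therefore already contains the entacapone contribution on a levodopa base of 1.00.

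**Step 2: the class split.** The entacapone part of the combination's LEDD is 0.33 / 1.33 = 0.248, about 25%. For an illustrative 600 mg levodopa per day:

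| Regimen | Levodopa class | COMT class | Total |
|---|---|---|---|
| Combination, SAP as written | 600 × 1.33 = 798 | 0 | 798 |
| Combination, split 1.00/0.33 | 600 × 1.00 = 600 | 600 × 0.33 = 198 | 798 |
| Levodopa/benserazide + separate entacapone | 600 × 1 = 600 | 198 | 798 |
| Levodopa/carbidopa + separate entacapone | 600 × 1.11 = 666 | 198 | 864 |

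Rows 1 and 3 have the same total and differ only in class. Row 4 differs from the combination by 864 − 798 = 66 mg in total. That gap comes from the 1.11 factor in Table 7-1, not from the class table.

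**Step 3: what a careless remedy would do.** Listing the tablet in both classes without splitting gives 798 + 198 = 996 mg, which counts the entacapone part twice.

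**Step 4: class use.** Shortfall in the COMT row = share of patients whose only COMT inhibitor is in the combination. For assumed shares, with 400 patients:

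- 2%: 2 percentage points, 8 patients
- 5%: 5 points, 20 patients
- 10%: 10 points, 40 patients
- 20%: 20 points, 80 patients

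**Step 5: can a reader recover the figure?** The combination has its own medication row, but some patients may take both it and a separate COMT inhibitor. If the COMT row shows 5% and the combination row 10% (assumed), the percentage on any COMT inhibitor lies between 10% (full overlap) and 5% + 10% = 15% (no overlap). The published rows give bounds; the patient-level data give the exact number.

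**Step 6: which other analyses use the class table?**

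- Total LEDD sums over medications, so it does not depend on class. The regression (SAP 7.8, Table 7-2) uses total LEDD.
- The primary variables (SAP 6.4) depend on whether any add-on is taken and, for the second definition, when it is taken. Class plays no part.
- Tapering, reasons and latency (SAP 6.5) are specified for each medication or therapy, not by class.

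**The case against.** One class per product is a legitimate convention, and the SAP discloses it by printing the table. The protocol's background (section 7.0) itself groups the combination with levodopa formulations when describing the pivotal trial. The combination has its own row, so the excluded patients are visible, and SAP 7.10 allows further analyses. All of this stands. It supports keeping the tablet under Levodopa, but it does not make the COMT row a count of patients on a COMT inhibitor, and the separate row cannot be added to it without double counting.

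It is also true that dual listing would need a rule for category total daily dose, and that the LEDD split does not make the combination equal to levodopa/carbidopa plus separate entacapone: the 66 mg difference at 600 mg remains.

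A reader might infer more than the documents support:

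- *That LEDD as such is wrong.* It is not. The 1.33 factor carries the entacapone part, so medication-level and total LEDD do not depend on the class table.
- *That false stops and starts in the tapering or latency analyses come from this mapping.* Those analyses are per medication. A change between presentations would show there as a change of product under any class table.
- *That the shortfall varies by country or over time.* It would if the tablet mix did, but the documents give no mix.

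**Conclusion.** The point holds for two sets of secondary descriptive rows: COMT-inhibitor use by class, and the division of LEDD between the Levodopa and COMT classes. The use row is understated by the share of patients whose only COMT inhibitor is in the combination. The figures of 2 to 20 percentage points illustrate assumed shares and are not estimates. In the LEDD rows, about 25% of the combination's LEDD sits under Levodopa; that proportion follows from Table 7-1 alone and needs no assumption about the mix.

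This is an attribution gap in a protocol-required output. It should not be read as a flaw in the primary result or in the predictor models, and describing the class table as an outright error would go too far. The change is worth making because it needs only data already collected and gives a number that the planned rows cannot give.

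**What to change.** In SAP 6.5, keep the combination under Levodopa and add a derived row, 'any COMT inhibitor, alone or in fixed combination', counting each patient once at each time point. A footnote should say that this row overlaps with Levodopa.

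If class LEDD is reported, state in SAP 7.6 that the combination contributes 1.00 × levodopa to the Levodopa class and 0.33 × levodopa to the COMT class. Total LEDD stays as defined, and no further 0.33 is added to the 1.33.

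Leave the category total daily dose rows as they are, with the tablet's levodopa milligrams under Levodopa only. The reasons analyses need no change because they are not specified by class.

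The cost is one extra derived row, a short rule for class LEDD, and class percentages that overlap, which the multiple-answer format already allows. No new data are needed. The 1.11 versus 1.00 difference in the levodopa factor belongs to Table 7-1 and is not resolved by this change.

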#### LCIG infusion:

At the time points LCIG initiation and at 3, 6, 9, and 12 months after LCIG initiation, at visit and at appropriate time points between 12 months after LCIG initiation and the visit:

- Total dose per day (in ml) with total dose per day calculated as morning dose
   + continuous dose x duration of infusion + extra dose.
- Morning dose (in ml)
- Continuous dose (in ml/h)
- Daily duration of infusion (in h/day)
- Daily duration of infusion in the following categories:
  - 0 <16 h/day

  - 16 <24h/day
  - 24h/day

For patients with a daily duration of 24h/day the dosing information will be listed

#### Tapering process:

- o For each add-on PD medication/therapy over all treatment phases:
  - Minimum total daily dose; if the add-on PD medication is stopped, the minimum total daily dose will be set to 0
  - Maximum total daily dose
  - The tapering process is any change in the dose concentration (decreasing or increasing dose) and the number of days for tapering process is the number of days between maximum and minimum daily dose; patients with minimum (or maximum, respectively) daily dose not at the end of the tapering process will be checked. A maximum duration of ca. 2 months of the tapering process is allowed (otherwise the tapering process is set to missing). Dates which are incomplete will not be imputed and, thus, no tapering process can be identified (missing). If the add-on PD medication is stopped, but no entry with

[figure not shown]
dose = 0 is recorded the stop date will be used as date of minimum total daily dose.

- For each add-on PD medication/therapy:
   Only for the time period of tapering process:
   If within the tapering process: at the time points LCIG initiation and at 3, 6, 9, and 12 months after LCIG initiation and at visit:
  - Total daily dose (except all 'Other', Anticholinergics, and Surgical therapy; Apomorphine only if possible)
  - Posology (i.e. number of intakes per day; except all 'Other' and Surgical therapy)

[figure not shown]

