9.2.7.5 Previous PD medication and add-on PD treatment during **LCIG Treatment**

Data on previous PD medication (right before initiation of LCIG treatment) will include date of drug initiation and/discontinuation, reason for its discontinuation, drug name, total dose per day, posology, and attempts of previous device-aided therapies (e.g., CSAI, DBS).

Data on add-on PD medication upon LCIG initiation or during LCIG treatment will include date of drug initiation/discontinuation, drug name, total dose per day, posology, tapering* process (duration and posology), starting and end date of LCIG titration, reasons for add-on drug therapy (severity and frequency), timing of add-on drug (during/outside of infusion hours).

Levodopa equivalent daily dose (LEDD) table published by Tomlinson, et al will be used to calculate LEDD. [47]. Each PD medication amount should be multiplied by the appropriate value to obtain the corresponding LEDD. Adding together the corresponding LEDD for each PD medication, will be providing the total LEDD.

9.2.7.6 **Concomitant Disease and Medication**

Information on concomitant disease and medication (non-PD treatment) will be collected and reported in the eCRF, including drug name, indication, start/stop date, and dosages.

^{*}The term "tapering" is used within this study in the context of drug treatment. It refers to the process of reducing a certain drug dosage incrementally (over a few days or weeks), instead of its abrupt discontinuation. For some PD medications a tapering process is needed to avoid a withdrawal syndrome

9.2.7.7 **LCIG Treatment**

Information on LCIG treatment from initiation until the day of the visit will be documented in the eCRF, including reason(s) for initiation of LCIG treatment, date of introduction of LCIG, use of nasojejunal tube, date of PEG-J procedure, date of titration and duration of titration process, infusion settings (infusion time, morning dose, continuous infusion rate, total daily dose) and dose modification (number of dosage changes, new infusion settings or temporary interruptions in LCIG daily infusion rate and reasons for dosage adjustment).

A LCIG substantial dose adjustment is defined as any increase or decrease of the total daily LCIG dose by more than 20% of total daily dose.

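### The SAP counts dose increases as tapering, against the protocol's definition, and sets spans over about 2 months to missing without a separate count

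*SAP*

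**What the plan says.** The protocol lists among its secondary endpoints (abstract and section 9.1) the "number of days required for the tapering process" for add-on medication. The footnote in Protocol 9.2.7.5 defines the term: "It refers to the process of reducing a certain drug dosage incrementally (over a few days or weeks), instead of its abrupt discontinuation".

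SAP 6.5, under Tapering process, defines it differently: "The tapering process is any change in the dose concentration (decreasing or increasing dose", with the parenthesis naming both directions. Duration is then fixed by the dose extremes: "the number of days for tapering process is the number of days between maximum and minimum daily dose". Those extremes are found "For each add-on PD medication/therapy over all treatment phases". If an add-on is stopped, its minimum is set to zero. Patients whose minimum (or maximum) does not fall at the end of the process are to be checked.

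Two rules produce missing durations. One is the cap: "A maximum duration of ca. 2 months of the tapering process is allowed (otherwise the tapering process is set to missing". The other concerns dates: "Dates which are incomplete will not be imputed and, thus, no tapering process can be identified (missing".

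SAP 7.1 summarises quantitative variables on valid values, with one count of missing values. SAP 6.7 covers only missing items in rating scales. SAP 2.5 says the plan agrees with the protocol and that substantial departures are described in detail. The text of 6.5 does not flag its definition as a departure.

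**The concern.** There are two separate problems.

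**Definition.** The protocol treats introducing and tapering an add-on as different events, and tapering means reduction. Under the SAP wording, an add-on raised from a low to a high dose within the allowed time yields a taper duration. Followed as written, the endpoint would describe a mixture of reductions and increases. A reader of the report, with the protocol in hand, would take it to describe reductions only.

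**Cap.** A duration is discarded because of its own value, and the discarded values join incomplete dates in one missing count. A reader could not see how many spans were removed for length, nor whether they were slow tapers or artefacts of the measure.

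What is at stake is one descriptive component of a secondary endpoint. How add-on medication is tapered is nevertheless part of the study's stated rationale, so the duration is likely to be read and cited.

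**Working it through.** The plan states no expected taper duration and no precision target for this endpoint, so there is no figure of its own to reproduce. The check has three parts.

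**1. Effect of including increases.** Let reductions number n_d with mean duration m_d, and increases n_i with mean m_i. The pooled mean is (n_d·m_d + n_i·m_i)/(n_d + n_i). It moves from m_d towards m_i, so the sign of the change is the sign of m_i − m_d. The documents give neither mean, so the direction is unknown. The exposure is limited in one respect: an add-on that is stopped for good has its minimum set to zero at the stop, so its maximum comes first and it is a reduction by construction. Increases enter through add-ons that were not stopped.

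**2. Effect of the cap on genuine tapers.** The inputs are:
- Cap: SAP 6.4 uses 30.4 days per month, so 2 × 30.4 = 60.8 days. Because the SAP gives the limit only approximately, 56 and 70 days were also tried.
- Durations: assumed log-normal with median M and log-SD s. The shape and both values are assumptions.

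With a = (ln 60.8 − ln M)/s:
- share removed = 1 − Φ(a)
- true mean = M·exp(s²/2)
- capped mean = true mean × Φ(a − s)/Φ(a)
- capped median = M·exp(s·Φ⁻¹(Φ(a)/2))

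Example, M = 14, s = 0.6: a = (4.1076 − 2.6391)/0.6 = 2.448 and 1 − Φ(a) = 0.007. True mean = 14·exp(0.18) = 16.8. Capped mean = 16.76 × 0.9677/0.9928 = 16.3.

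Example, M = 42, s = 0.7: a = (4.1076 − 3.7377)/0.7 = 0.528 and 1 − Φ(a) = 0.299. True mean = 42·exp(0.245) = 53.7. Capped mean = 53.66 × 0.4319/0.7014 = 33.0.

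| M (days) | s | Removed | Mean, true → capped | Median, true → capped |
|---|---|---|---|---|
| 14 | 0.6 | 0.7% | 16.8 → 16.3 | 14 → 13.9 |
| 14 | 1.0 | 7.1% | 23.1 → 16.9 | 14 → 12.8 |
| 30 | 0.6 | 12.0% | 35.9 → 29.3 | 30 → 27.4 |
| 30 | 1.0 | 24.0% | 49.5 → 25.0 | 30 → 22.1 |
| 42 | 0.7 | 29.9% | 53.7 → 33.0 | 42 → 32.1 |

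Moving the cap from 56 to 70 days changes the share removed from 1.0% to 0.4% in the first row and from 26.6% to 19.8% in the fourth.

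**3. Effect of the cap on spans that are not tapers.** Every patient has at least 12 months on LCIG, and the extremes are taken over the whole period. A high dose early and a stop much later gives a very long span without any continuous taper. As an illustration, take 80% genuine tapers (log-normal, median 14 days, log-SD 0.7) and 20% spurious spans spread evenly over 61 to 730 days:
- genuine tapers alone: mean 14·exp(0.245) = 17.9 days, median 14.0
- with the cap: mean 16.7, median 13.8
- without the cap: mean 0.8 × 17.9 + 0.2 × (61 + 730)/2 = 14.3 + 79.1 = 93.4, median 17.5

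In this case the capped result is much closer to the truth than the uncapped one.

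**The case against.** The strongest defence is that the cap is a validity rule. The protocol itself speaks of a process lasting days or weeks, and a measure running from maximum to minimum over all treatment phases will pick up spans that no clinician would call a taper. A limit of about 2 months screens these out, and removing it without changing the measure could bias durations upward, as part 3 shows. This stands. It does not fully answer the point, because the rule cannot separate a slow but genuine taper from an artefact, and the SAP does not plan to count or examine what it removes.

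A reader might infer that reported durations are necessarily too short, so that the study would show faster tapering than occurred. The documents do not support that. Only the cap has a known direction, and only for genuine tapers beyond it; including increases could move the result either way.

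The defence can also say that the SAP plans a check on where the minimum or maximum falls, that missing N is reported, and that the SAP does not expressly say increases and decreases will be pooled in one summary. The check shows that both directions are intended, but the text provides no split between them. Missing N makes exclusions visible but not their reason. Figures in that section could not be read and might clarify the rule. Finally, SAP 7.10 calls the study exploratory, and no test, primary estimate or sample size depends on this variable. That limits the weight of the point but does not remove the contradiction.

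**Conclusion.** The definition problem is established from the text: SAP 6.5 includes dose increases in an endpoint that Protocol 9.2.7.5 restricts to reductions, and the departure is not flagged. Its effect on the reported duration has unknown direction and size.

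The cap problem is established as a reporting gap. Spans over about 2 months are removed by their own value and cannot be told apart from incomplete dates. Any genuine taper beyond the cap is lost, which lowers the mean and lowers or leaves unchanged the median. Under the assumed log-normal durations the loss runs from about 1% of tapers (median 14 days, log-SD 0.6) to about 30% (median 42 days, log-SD 0.7). With tapers around two weeks and modest spread the distortion is trivial. Because the same rule also removes spans that are not tapers, the net bias cannot be derived from the documents.

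The primary endpoint and the planned 400 patients are unaffected. The point is worth correcting before analysis but is not critical.

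**What to change.** - Reconcile SAP 6.5 with Protocol 9.2.7.5: count a taper only when the maximum dose precedes the minimum within one continuous run of dose reductions. Requiring the order alone is not enough, because a high dose early and a stop years later would still qualify. Report dose increases in a separate summary.
- State the cap in days, so that it can be programmed.
- Report the number of spans over the cap separately from the number lost to incomplete dates.
- Check each span over the cap to see whether it is a continuous reduction. Show the duration summary with and without the verified tapers over the cap. Do not simply restore all long spans.
- Record the change of definition as SAP 2.5 requires.

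The cost is SAP wording, a little extra programming and a review of the long spans. The dose and date records that SAP 6.5 already uses are enough.

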#### 4.2.1 Inclusion criteria

Patients were eligible for study participation if all of the following criteria were fulfilled:

- 1. Patients diagnosed with APD and on LCIG treatment for at least 12 months
- 2. Patient must have been on continuous LCIG treatment for at least 80% of days in the preceding year
- 3. Patients must be treated by the same physician (PI or co-investigator) since the initiation of LCIG treatment
- 4. Decision to treat with LCIG was made and therapy was started by the physician prior to any decision to approach the patient to participate in this study
- 5. Prior to any data collection, the patient, or legal authorized representative (LAR) has voluntarily signed an Authorization for Use/Disclosure of Data (AUDD)/informed consent form (ICF) according to national regulations after the study has been explained and the subject has had the opportunity to have questions answered

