#### 6.4 Primary variable

There are two primary variables:

1. LCIG monotherapy 1 (yes, no) at LCIG initiation and at 3, 6, 9, and 12 months after LCIG initiation

with the following definition:

- LCIG monotherapy means that the patient is not on any add-on PD medication or PD therapy at the respective time point.
- 2. LCIG monotherapy 2 (yes, no) at LCIG initiation and at 3, 6, 9, and 12 months after LCIG initiation

with the following definition:

LCIG monotherapy means that the patient is allowed to take an add-on PD medication or PD therapy at the respective time point, however, only in the evening after the LCIG infusion is completed (i.e. reason for start of add-on PD medication: other).

Additional specifications for both variables are:

- Medications for indications secondary to PD are allowed.
- If the reason for add-on PD medication is missing the medication will be considered as taken during LCIG infusion (i.e. no monotherapy).
- LCIG initiation date is the start date of the first LCIG infusion.
- 3 months after LCIG initiation is calculated as LCIG initiation date + rounded (3 [months] x 30.4 [days]). 6, 9, and 12 months after LCIG initiation will be calculated analogously.
- For LCIG initiation date with missing day the 15th will be used.

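### SAP 6.5 reads in-taper dose and posology only at fixed dates at least 91 days apart, or at the visit, while a valid taper lasts at most about 2 months

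*SAP*

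**What the plan says.** The protocol makes tapering a secondary endpoint (section 9.1, repeated in the Abstract): "number of days required for the tapering process, total dose per day and posology for add-on PD medication prior to LCIG initiation", and likewise at initiation (titration) and during ongoing LCIG treatment. The footnote in Protocol 9.2.7.5 describes tapering as a stepwise dose reduction that takes days or weeks.

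SAP 6.5, Tapering process, handles this in two parts.

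- **Per drug, over all treatment phases.** The SAP takes the minimum total daily dose (0 if the drug is stopped), the maximum total daily dose, and the number of days between them. On length it says: "A maximum duration of ca. 2 months of the tapering process is allowed (otherwise the tapering process is set to missing").
- **Within the taper.** Under the restriction "Only for the time period of tapering process", total daily dose and posology are read by this rule: "If within the tapering process: at the time points LCIG initiation and at 3, 6, 9, and 12 months after LCIG initiation", and also at the visit.

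SAP 6.4 converts months to days by multiplying by 30.4 and rounding. The visit comes no earlier than 12 months after the start of LCIG (SAP 4.2.1: "Patients diagnosed with APD and on LCIG treatment for at least 12 months"). For add-on medication and LCIG infusion, SAP 6.5 also allows suitable time points between month 12 and the visit. The tapering part does not.

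**The concern.** The planned reading dates are further apart than the longest taper the SAP accepts. Whether a taper contributes a dose or posology value then depends on where it falls in the calendar, and longer tapers are more likely to be caught than short ones. A taper that does contribute usually does so at one arbitrary point along its course.

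No reading date precedes day 0, although the protocol endpoint names the period before LCIG initiation. After month 12 the only reading is at the visit.

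How add-on drugs are handled around LCIG initiation is part of the study rationale (Protocol 7.0). At stake is whether the in-taper tables can describe dose and posology by phase, as the endpoint asks.

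**Working it through.** The plan gives no share of tapers with a reading, so there is no figure of its own to reproduce.

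**Inputs**

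- Reading dates, from SAP 6.4: round(3 × 30.4) = 91, round(6 × 30.4) = 182, round(9 × 30.4) = 274, round(12 × 30.4) = 365, plus day 0 and the visit. The gaps are 91, 91, 92 and 91 days.
- Longest valid taper, from SAP 6.5: about 2 months, taken as 2 × 30.4 ≈ 61 days.
- Taper start and length: not given in the documents. Assumption: starts uniform over days 1 to 365, with lengths L from 7 to 61 days. L is the last day minus the first, matching the SAP's count of days between maximum and minimum dose.

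**Step 1: two planned readings.** A taper must span at least the smallest gap, so L ≥ 91. The cap is about 61, so a valid taper wholly within the first year contains at most one planned date. The visit creates one exception: a taper that starts in the first year and runs past day 365 to a visit on days 366 to 426 can contain both.

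**Step 2: no reading.** A taper starting on day s has none if no reading date lies in s to s + L. Every taper starting on days 1 to 30 with L ≤ 56 ends by day 86 and so has none. A taper finished before day 0 has none either.

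**Step 3: share with a value, starts on days 1 to 365.** Each of the four dates (91, 182, 274, 365) is covered by L + 1 start days, and these sets do not overlap when L ≤ 90. The share is 4(L + 1)/365.

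| L (days) | Calculation | With a value | Without |
|---|---|---|---|
| 7 | 32/365 | 8.8% | 91.2% |
| 14 | 60/365 | 16.4% | 83.6% |
| 30 | 124/365 | 34.0% | 66.0% |
| 44 | 180/365 | 49.3% | 50.7% |
| 45 | 184/365 | 50.4% | 49.6% |
| 60 | 244/365 | 66.8% | 33.2% |
| 61 | 248/365 | 67.9% | 32.1% |

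Break-even is at L of about 45 days, a little over 6 weeks.

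**Step 4: starts spread over the whole follow-up.** With a visit on day V well after month 12 there are five dates, so the share is 5(L + 1)/V.

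| Visit (assumed) | L = 28: without a value | L = 61: without a value |
|---|---|---|
| Day 730 | 1 − 145/730 = 80.1% | 1 − 310/730 = 57.5% |
| Day 1095 | 1 − 145/1095 = 86.8% | 1 − 310/1095 = 71.7% |
| Day 1825 | 1 − 145/1825 = 92.1% | 1 − 310/1825 = 83.0% |

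**The case against.** The strongest reply is that much of the dose information does not depend on the reading dates. For an ordinary downward taper, the maximum dose, the minimum dose and the days between them are the starting dose, the final dose and the length. SAP 6.5 also gives dose and posology per drug at the fixed time points, and time to start or change of each drug. This stands, with limits. The maximum and minimum are taken per drug over all phases, so they separate neither the protocol's phases nor repeated tapers of one drug. They carry no intermediate step, and posology has no counterpart.

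A reader might infer that most tapers give no value because of the 2-month cap. That does not follow: at the cap, about two thirds of first-year tapers do give one. It takes the further premise of tapers shorter than about 6 weeks, very early starts, or long follow-up. The protocol's description of tapering supports the first premise but gives no distribution.

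A reader might also infer that the tables will be mostly empty, or that nothing about tapering can be learned. Neither is shown. Tapers running on the initiation day always get one reading and are left out of the calculation above. Protocol 7.0 places much tapering around titration, so they may be common; equally, tapers starting just after day 0 would be missed.

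The endpoint can also be read as dose by phase rather than a step-by-step schedule. Even so, the fixed dates include none before initiation and do not follow the phases.

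Finally, this is a descriptive secondary variable with no bearing on the primary endpoint, and SAP 7.10 permits extensions. That limits the weight of the point. It does not supply the missing rule.

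**Conclusion.** The concern holds for the in-taper readings of dose and posology. Three statements need no assumption about when tapers start:

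- a taper lying between two reading dates yields nothing;
- a taper completed before LCIG initiation yields nothing;
- a valid taper wholly within the first year yields at most one planned value.

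The size of the loss does rest on an assumption. With starts uniform over days 1 to 365, about 9% of 7-day, 16% of 14-day, 34% of 30-day and 67% of 60-day tapers yield a value, so tapers shorter than about 6 weeks mostly yield none. The loss concerns posology, intermediate doses and the split by phase. Taper length and the pooled maximum and minimum dose remain available.

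**What to change.** For this endpoint, replace the fixed dates with dates tied to the taper. For each taper, report total daily dose and posology on its first day, at each recorded step and on its last day. Group tapers by the protocol's phases: before LCIG initiation, at initiation (titration), and during ongoing LCIG. Keep months 0, 3, 6, 9 and 12 and the visit for the add-on status tables.

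The cost is SAP wording and extra table shells. SAP 6.5 already finds the dates of maximum and minimum dose from dated records, so no new collection is implied. Protocol 9.2.7.5 lists taper duration and posology under add-on medication from initiation onwards, and only start and stop dates, dose and posology for earlier medication. Steps before initiation may therefore be sparse, and the tables should show how many tapers lack dated steps in each phase.
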